## **8 Measurements and procedures**

This is a crossover design in which participants will spend two weeks wearing devices that are professionally programmed according to the participant's audiogram, and two weeks wearing devices that are entirely self fit. The order of fitting will be randomized in a 1:1 allocation ratio.

Participants will complete the QuickSiN speech test in all three conditions: unaided, aided with professional fitting, and aided with self-fitting. They will also complete the APHAB questionnaire in all three conditions.

Real Ear Aided Responses (REAR) will be measured following the initial fittings as well as at each follow up visit.

See table below for schedule of events.

Appointment	Trial Day	Variables recorded
1	1	
 
• Unaided APHAB
 
• Unaided QuickSiN
 
• Initial fittings for both treatments
 
• REAR for both treatments
 

2	2-7	N/A: First set of devices dispensed following a wash-out period
3	16-21	
 
• Adverse Event assessment
 
• APHAB with first treatment
 
• QuickSiN with first treatment
 
• REAR with first treatment
 
• Blinding assessment
 

4	30-35	
 
• Adverse Event assessment
 
• APHAB with second treatment
 
• QuickSiN with second treatment
 
• REAR with second treatment
 
• Blinding assessment
 

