## 9 Statistical design and analysis

Sample size is driven by the difference in APHAB global benefit scores between self-fitting and the professionally-fitted hearing aid. Assuming that the average difference score,  $APHAB_{self} - APHAB_{prof}$  is -5.0, and the standard deviation of the difference score is 14, 40 subjects with APHAB global scores in both periods are needed to demonstrate with 90% power the non-inferiority against the margin of -12.5 using Mixed Model ANOVA, setting one-tailed  $\alpha=0.025$ .

Anticipating an attrition rate of no more than 10%, to minimize the impact of imputed data on the overall efficacy conclusion, 44 subjects will be enrolled and those randomized will enter into the Intent to Treat population.

In terms of examining safety, the proportion of subjects experiencing any Adverse Device Effect will be a key safety endpoint. A sample size of 40 provides a 95% Clopper-Pearson confidence interval with a half-width no wider than 0.133 when the observed sample proportion is 0.20 or less. In other words, we can be 95% confident that the true population proportion of Adverse Device Effects is no greater than 0.133 larger than the observed sample proportion when the sample size is 40 and the sample proportion is 0.20 or less.

Note that this sample size is slightly higher than that included in 510(k) K213424, which included the same endpoints and a similar crossover design.

The analysis populations are as follows:

Intent to Treat: All participants randomized.

Safety: All participants randomized who receive one or more study device kits.

Data will be entered immediately following participant completion of the assigned tasks. Unaided and both aided responses will be analyzed for each participant for the APHAB global benefit and dB SNR loss scores. The two aided conditions will be analyzed for non-inferiority as per the statistical plan.

The APHAB global benefit score recorded during the self-fitting will be compared to the APHAB global benefit score recorded during the professional-fitting by way of a 2-period, crossover, repeated measures mixed model, where APHAB score is the dependent variable, treatment sequence is the between-subjects factor, Period is the within-subjects factor and treatment (Self-Fit/Professional-Fit) is the repeated measures factor.

The hypotheses are:  $H_0: \mu_{\text{self}} - \mu_{\text{prof}} < -12.5$   $H_a: \mu_{\text{self}} - \mu_{\text{prof}} \geq -12.5$ ,

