where  $\mu_{\text{self}}$  represents the mean APHABself score in the population and  $\mu_{\text{prof}}$  represents the mean APHABprof score in the population.

The observed treatment effect will be compared to the non-inferiority margin of -12.5 by way of pre-planned TEST or ESTIMATE statements using SAS PROC GLM or PROC MIXED.

The carryover effect will be tested by means of a RANDOM statement on the subject nested within sequence effect.

The planned analysis will be done by an expert biostatistician who has previous experience with FDA clinical trials.

The dB SNR loss score recorded during the self-fitting will be compared to the dB SNR loss score recorded during the professional fitting by way of a 2-period, crossover, repeated measures mixed model, where dB SNR loss score is the dependent variable, treatment sequence is the between-subjects factor, Period is the within-subjects factor and treatment (Self-fit/Professional-Fit) is the repeated measures factor.

The carryover effect will be tested by means of a RANDOM statement on the subject nested within sequence effect.

All analyses will be completed by an expert biostatistician who has previous experience with FDA clinical trials.

At each return lab visit, the sub-investigator A will notate any device deficiencies or possible adverse events as reported by the participant in the participant study folder.

If any AE are reported, the severity and scope will be reviewed and the study manager/sponsor, along with the PI will decide on the appropriate follow up.

Treatment-emergent Adverse Events will be attributed to the treatment condition (self-fit or professional fit) of the device being evaluated. The number and proportion of subjects reporting any Adverse Event, any Adverse Device Effect, any Serious Adverse Event, or any Serious Adverse Device Effect will be summarized by treatment condition and overall. The incidence of Adverse Events by AE term will be summarized by treatment condition and overall.

Missing aided APHAB global benefit scores and dB SNR loss scores for either visit 3 or 4 will be subjected to multiple imputation. Originally, missing data is assumed to be monotone and Missing at Random (MAR). Multiple imputation approach will follow fully-conditional specifica-

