## **10 Investigation Duration**

The total expected duration of the clinical investigation is six months, with the expected duration for each participant to be 5 weeks.

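### Does the plan's carryover test, worded as a RANDOM statement on subject within sequence, fail to test carryover?

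*Combined protocol and SAP*

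**What the plan says.** Section 9 specifies a crossover mixed model for the APHAB global benefit score in which "treatment sequence is the between-subjects factor, Period is the within-subjects factor and treatment (Self-Fit/Professional-Fit) is the repeated measures factor". The QuickSiN model has the same form: "where dB SNR loss score is the dependent variable, treatment sequence is the between-subjects factor". For each endpoint a separate sentence then covers carryover: "The carryover effect will be tested by means of a RANDOM statement on the subject nested within sequence effect". The treatment effect is compared with the margin "by way of pre-planned TEST or ESTIMATE statements using SAS PROC GLM or PROC MIXED".

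Two entries in the section 8 schedule bear on how likely carryover is. Appointment 1 includes "Initial fittings for both treatments", and the entry for appointment 2 reads "First set of devices dispensed following a wash-out period". Section 10 gives the length of participation: "with the expected duration for each participant to be 5 weeks".

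**The concern.** The only effect that the carryover sentences name is subject nested within sequence. A test of that term asks whether participants differ from one another, which they almost always do. It carries no information on whether one fitting influences the period after it. On that reading, a significant result caused by ordinary differences between people could be reported as carryover, and true carryover would go unseen.

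The sentences also state no significance level and no consequence. The subject matters in this trial because the schedule names a wash-out only before the first devices. If one fitting carries over more than the other by some number of points, the estimated difference between self-fitting and professional fitting moves by half that number. The plan allows only 7.5 points between the assumed difference (-5.0) and the margin (-12.5).

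**Working it through.** **Inputs.** From section 9: assumed difference -5.0, margin -12.5, SD of the within-subject difference 14, one-sided alpha 0.025, 40 subjects. From section 8: 1:1 allocation, hence 20 per sequence. The correlation ρ between a participant's two aided scores is not in the documents; 0.3, 0.5 and 0.7 are assumed. The carryover sizes are hypothetical.

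**The plan's own figure.** The distance to the margin is 12.5 - 5.0 = 7.5. The normal approximation gives (14 × (1.960 + 1.282) / 7.5)² = 36.6, so 37 subjects. The noncentral t with N - 2 degrees of freedom gives 39, and power at 40 is 0.910. The stated 40 subjects for 90% power is reproduced. The carryover sentences play no part in it.

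**Where carryover appears.** Add each participant's two scores. Each treatment and each period enters that total once in either sequence, so both cancel when the sequence means are compared. What remains is the difference in carryover, λ, aliased with treatment-by-period interaction and with any chance difference between the two groups. The effect that reflects λ is therefore sequence. Its natural error is the spread of the totals among participants within a sequence, which is subject(sequence).

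**Two readings on one data set (40 subjects, carryover added in steps).**

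| λ (points) | F for subject(sequence) | F for sequence against subject(sequence) |
|---|---|---|
| 0 | 2.6641 | 0.10 |
| 5 | 2.6641 | 1.21 |
| 10 | 2.6641 | 3.52 |
| 15 | 2.6641 | 7.05 |
| 25 | 2.6641 | 17.74 |
| 50 | 2.6641 | 65.67 |

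The first F never moves because the sequence means are removed before it is formed. The second responds as a carryover test should. A REML mixed model with sequence fixed and subject random gave the same sequence F (0.103 at λ = 0, 17.743 at λ = 25).

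**Is the named term the right one?** In 20,000 simulated trials per setting with no carryover, testing sequence against subject(sequence) at two-sided 0.05 rejected 5% of the time at every ρ. Testing it against the within-subject residual rejected 14.5%, 25.4% and 39.5% of the time at ρ = 0.3, 0.5 and 0.7. Declaring subject(sequence) random is what avoids that error.

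**What the valid test can show.** The variance of the total is 196 × (1 + ρ)/(1 - ρ), so the SE of the sequence contrast is 14 × √[(1 + ρ)/(1 - ρ)] × √(2/20), and the 95% half-width is 2.024 times that.

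| ρ | SE | 95% half-width | Power at λ = 10, two-sided 0.05 |
|---|---|---|---|
| 0.3 | 6.03 | 12.2 | 37% |
| 0.5 | 7.67 | 15.5 | 25% |
| 0.7 | 10.54 | 21.3 | 15% |

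This imprecision belongs to any crossover of this form and size. The wording does not cause it, and rewording would not reduce it.

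**Schedule.** The visit windows are 14 days apart at both ends (16 - 2, 21 - 7, 30 - 16, 35 - 21), and 7 + 14 + 14 = 35 days, or 5 weeks. Appointments 3 and 4 can be 30 - 21 = 9 to 35 - 16 = 19 days apart. A gap between treatments is possible for some participants, but none is named.

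**The case for a change.** The strongest reply is that a generous reading supplies the effect but not the level or the consequence. Whether a positive result would prompt a further analysis is left open until the data are in, in a study meant to support a regulatory submission. Carryover could also do damage. The crossover SE is 14/√40 = 2.21. If the true difference sat exactly at -12.5 and a 10-point carryover difference favoured self-fitting, the estimate would shift by 5 points and the chance of wrongly concluding non-inferiority would rise from 2.5% to about 60%. For a 5-point carryover difference it would be about 20%.

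The factual part stands: effect, level and use are not stated, and the documents name no wash-out between treatments. But the risk just described comes from the design and is the same however the sentence is worded. A named test with 15% to 37% power at 10 points would not guard against it. Adding a period-1-only estimate would not settle the matter either. Its SE is √(196/(2(1 - ρ))) × √(2/20) = 3.74, 4.43 or 5.72. At the planned difference of -5 its expected lower 95% limit is then -12.6, -14.0 or -16.6, beyond the margin even with no carryover.

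Nor does allowing PROC MIXED make the wording worse. A RANDOM statement on its own gives only a variance component, but the plan does not use it on its own, because sequence is a factor in both models. Finally, both fittings are made at appointment 1, before either device has been worn at home, which closes one obvious route for carryover. It does not rule out adaptation during wear.

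**Conclusion.** The concern does not hold as a fault in the analysis. The sentences describe the means of testing carryover, and the means named is the correct error term for the sequence effect that the models already contain. PROC GLM (with the TEST option on its RANDOM statement) or PROC MIXED then gives a valid sequence test. What is missing is detail that the experienced biostatistician assigned to the analysis would supply in the ordinary way.

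The effect on the primary result is nil. The sample size of 40 reproduces, the treatment model is unaffected, and the comparison with -12.5 goes ahead whatever the carryover test shows. The plan contains no two-stage rule, and nowhere says that a non-significant result will be taken to show absence of carryover. With half-widths of 12.2 to 21.3 points, such a claim could not be supported.

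This conclusion depends on reading the carryover sentences together with the model statements in section 9. The precision figures also depend on the assumed correlations of 0.3 to 0.7 and equal sequence sizes. No corresponding figures can be given for QuickSiN, since the documents state no SD for it, but the argument about the error term is the same.

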## 2 Objectives

The primary effectiveness objective of this investigation is to demonstrate that individuals age 18+ with self-perceived mild to moderate hearing loss are able to achieve non-inferior APHAB-global benefit scores when using a device fit with Sonova's self-fitting method compared to the same device fit by a professional.

The secondary effectiveness objective of this investigation is to demonstrate that individuals age 18+ with self-perceived mild to moderate hearing loss are able to achieve non-inferior dB SNR (Signal-to-Noise Ratio) loss scores as measured by the QuickSiN test, when using a device fit with Sonova's self-fitting method compared to the same device fit by a professional.

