## **6 Endpoints**

Primary effectiveness endpoint: Abbreviated Profile of Hearing Aid Benefit (APHAB) global benefit score, which is derived by subtracting the aided APHAB global score from the unaided APHAB global score. The APHAB is an externally developed and validated questionnaire that is available for use by both researchers and clinicians to assess hearing aid benefit (Cox and Alexander, 1995). The measure comprises 24 items distributed equally across four subscales ('Ease of Communication,' 'Reverberation,' 'Background Noise,' and 'Aversiveness'). These subscales were designed to assess the benefits of hearing aids for speech communication in a variety of listening environments, in addition to capturing the impact of bothersome loud sounds.

Secondary effectiveness endpoint: dB SNR loss score. QuickSiN, the testing procedure that measures dB SNR loss, is an adaptive test of an individual's ability to understand speech in noise. The test adapts the relative levels of noise and speech to determine the signal-to-noise ratio (SNR) at which the individual can correctly identify 50% of key words. This test was independently developed and validated and is available for use by clinicians and researchers (Killion, et al., 2004).

These outcomes closely match those of a recent study for a product cleared under the Self-Fitting Hearing Aid classification 510(k) K213424.

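### The secondary non-inferiority claim on dB SNR loss has no margin, so the planned analysis has nothing to be judged against

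*Combined protocol and SAP*

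**What the plan says.** Section 2 (Objectives) makes the secondary objective a demonstration that self-fit users "are able to achieve non-inferior dB SNR (Signal-to-Noise Ratio) loss scores as measured by the QuickSiN test", relative to the same device fitted by a professional. Section 9 repeats the intention. It first says "Unaided and both aided responses will be analyzed for each participant for the APHAB global benefit and dB SNR loss scores", and then "The two aided conditions will be analyzed for non-inferiority as per the statistical plan".

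For the primary endpoint, Section 9 supplies every element of a non-inferiority test. Forty participants are "needed to demonstrate with 90% power the non-inferiority against the margin of -12.5 using Mixed Model ANOVA, setting one-tailed" alpha of 0.025. A null and an alternative hypothesis are written for the mean APHAB scores, and "The observed treatment effect will be compared to the non-inferiority margin of -12.5 by way of pre-planned TEST or ESTIMATE statements".

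For the secondary endpoint, Section 9 says that "The dB SNR loss score recorded during the self-fitting will be compared to the dB SNR loss score recorded during the professional fitting" by the same kind of two-period crossover mixed model, with the same carryover test. Missing values are covered as well: "Missing aided APHAB global benefit scores and dB SNR loss scores for either visit 3 or 4 will be subjected to multiple imputation". There the specification ends. It contains no hypotheses, no margin and no step comparing the estimate with a margin.

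Section 6 defines the scale. QuickSiN is used to "determine the signal-to-noise ratio (SNR) at which the individual can correctly identify 50% of key words".

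**The concern.** A non-inferiority conclusion needs a stated amount by which the new method may be worse. The plan promises that conclusion for dB SNR loss and does not give the amount. As written, the model will produce an estimated difference and an interval, but no rule says which intervals count as success.

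The APHAB margin cannot fill the gap. It is in questionnaire points, the hypotheses that use it are defined on APHAB means, and its sign is wrong for this scale. APHAB benefit is better when higher, so its margin is negative. A higher dB SNR loss means that the listener needs a more favourable signal-to-noise ratio, which is worse, so the dB test needs a positive upper margin.

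At stake is one of the two stated effectiveness objectives of a study meant to support a 510(k) application (Section 1). If the margin is picked once the dB results are known, it can be picked to fit them.

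**Working it through.** **Inputs from the documents (Section 9).** 40 evaluable participants, two-period crossover, one-tailed alpha 0.025; for APHAB, margin -12.5, expected difference -5.0, SD of the difference 14.

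**Assumed inputs.** The documents give no SD and no margin on the dB scale. I take the SD of the paired dB difference as 1, 2, 3 or 4 dB, and use 1 dB and 2 dB margins only to show sensitivity; neither is a recommendation.

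**1. Reproduce the primary figure.** The distance from the expected difference to the margin is 12.5 - 5.0 = 7.5.
- Normal approximation: n = [14 × (1.960 + 1.282) / 7.5]² = 36.6, so 37.
- Noncentral t with n - 2 degrees of freedom: 38 participants give 89.5% power, 39 give 90.3% and 40 give 91.0%.

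The stated 40 participants and 90% power are therefore consistent with a t-based calculation. No such figure exists for dB SNR loss to reproduce.

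**2. Formulas for the dB scale.** SE = SD/√40, and t(0.975, 38) = 2.0244.
- Half-width of the 95% interval = 2.0244 × SE. This is also the observed self-fit advantage needed to bring the upper limit down to 0.
- Upper limit = observed difference (self minus professional) + half-width.
- P(upper limit ≤ 0) = P(T > 2.0244), where T is noncentral t with 38 df and noncentrality -(true difference)/SE.
- A 1 dB margin fails and a 2 dB margin passes when the observed difference lies from 1 - half-width up to 2 - half-width.

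**3. Results.**

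| Assumed SD (dB) | Half-width (dB) | P(upper limit ≤ 0), true difference 0 | P(upper limit ≤ 0), self-fit truly 0.5 dB worse | Upper limit if 0.5 dB is observed (dB) | Observed differences that fail 1 dB and pass 2 dB |
|---|---|---|---|---|---|
| 1 | 0.32 | 2.5% | <0.001% | 0.82 | 0.68 to 1.68 |
| 2 | 0.64 | 2.5% | 0.02% | 1.14 | 0.36 to 1.36 |
| 3 | 0.96 | 2.5% | 0.14% | 1.46 | 0.04 to 1.04 |
| 4 | 1.28 | 2.5% | 0.32% | 1.78 | -0.28 to 0.72 |

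An upper limit at or below 0 is the one outcome that establishes non-inferiority whatever the margin, because it lies below every positive margin. It amounts to showing that self-fit is better. For all other outcomes the margin decides. With an observed deficit of 0.5 dB, the SD 1 case passes both illustrative margins, and the SD 2, 3 and 4 cases fail 1 dB and pass 2 dB.

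**4. Margins that 40 participants could support.** At zero true difference, 90% power needs a margin of 0.526 SD: 0.53, 1.05, 1.58 or 2.10 dB for SDs of 1 to 4 dB. If the true deficit were 40% of the margin, the proportion planned for APHAB (5.0/12.5), the margin must be 0.526/0.6 = 0.877 SD: 0.88, 1.75, 2.63 or 3.51 dB.

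**The case against.** The strongest reply has four parts.

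- **The margin may be elsewhere.** Section 9 refers to a statistical plan, which could be a separate document. But the file is itself the combined protocol and SAP, Section 9 is its statistical section, and no other plan is named. The secondary paragraph shows no redaction or break. Sections 6 and 9 cite an earlier 510(k) with the same endpoints, but adopt no dB margin from it. What stands is a caveat: the margin is absent from this document, and a separate plan dated before unblinding would answer the point.
- **The rest can be inferred.** This is partly right. Direction follows from the scale in Section 6, and the one-sided 0.025 level could be carried over from the primary. Both should still be written down. The margin cannot be inferred from anything in the document.
- **It is only a secondary endpoint.** The sample size rests on APHAB, nothing makes overall success depend on the dB result, and the dB estimate and interval can be reported regardless. This limits the reach of the defect. It does not supply a success criterion for an objective worded as a demonstration.
- **The dB figures are assumed.** They are. They also take 40 complete pairs and 38 degrees of freedom, so they are approximate for an analysis pooled over imputations. The 2.5% figure holds for any SD.

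**Conclusion.** The concern holds. As written, the secondary analysis cannot support its non-inferiority conclusion unless the upper 95% limit is at or below 0. That happens 2.5% of the time if the two fittings are equal, and less than 0.4% of the time if self-fit is truly 0.5 dB worse with an SD of the difference between 1 and 4 dB. In every other case the conclusion rests on a margin not yet chosen, and for the assumed SDs a 1 dB-wide band of observed differences gives opposite answers at 1 dB and 2 dB. The defect must be fixed because it cannot be credibly repaired once the data are seen. It is confined to the secondary claim: the primary APHAB analysis, the sample size and the safety analysis stand.

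**What to change.** Before unblinding, add the following to Section 9, with matching wording in Section 2:

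- A margin delta > 0 in dB, with its justification.
- Hypotheses on dB SNR loss: H0: mu_self - mu_prof ≥ +delta against Ha: mu_self - mu_prof < +delta, at one-sided 0.025.
- The decision rule: conclude non-inferiority if the upper limit of the two-sided 95% confidence interval from the planned mixed model, pooled over imputations by Rubin's rules, is below delta.
- The power at n = 40 for the chosen delta and an assumed SD.

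I would also test the secondary claim only after the primary succeeds. This is a separate multiplicity choice. Two unordered tests at 0.025 allow up to 0.025 + 0.025 = 5.0% for at least one false claim; the fixed order holds it to 2.5%.

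If no margin can be justified, restate the secondary objective as estimation of the difference with a 95% confidence interval and make no non-inferiority claim.

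The change is a few sentences, with no extra participants or data. Its real cost is commitment. The margin may have less than 90% power: at zero true difference and n = 40, power for a 1 dB margin is 87%, 54% or 34% for assumed SDs of 2, 3 or 4 dB, and for a 2 dB margin it is above 99%, 98% or 87%. Ordered testing forfeits the secondary claim if the primary fails, and the estimation route gives that claim up altogether.

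### The plan does not ensure that a failed self-fitting counts against the self-fitting method in the primary comparison

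*Combined protocol and SAP*

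**What the plan says.** All references are to the combined protocol and SAP.

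- **Objective (section 2).** The aim is to show that adults with self-perceived mild to moderate loss "are able to achieve non-inferior APHAB-global benefit scores when using a device fit with Sonova's self-fitting method", compared with the same device fitted by a professional.
- **Schedule (section 8).** Appointment 1 on day 1 includes "Initial fittings for both treatments", together with the unaided APHAB and unaided QuickSIN. The first devices are dispensed at appointment 2 (day 2-7). Aided scores are taken at appointments 3 and 4. The order of fitting is randomized 1:1, but the section does not say when.
- **Population (section 9).** "Intent to Treat: All participants randomized". The text separates the 44 people enrolled from those randomized, and only the latter form this population.
- **Missing scores (sections 9).** "Missing aided APHAB global benefit scores and dB SNR loss scores for either visit 3 or 4 will be subjected to multiple imputation". The data are taken to be monotone and MAR. Imputation is by chained equations, at least 100 times, combined by Rubin's rules. A pattern-mixture sensitivity analysis is named without a shift, a reference pattern or a tipping point.

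The documents give no rule or score for a participant who cannot complete the self-fitting, and plan no count of how many complete it.

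**The concern.** The objective is about what people can achieve when they fit the device themselves. Being unable to produce a usable fitting is therefore a result of the method under test. The plan leaves two routes by which that result can drop out of the primary analysis.

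1. If randomization follows the appointment 1 fittings, a person whose self-fitting fails that day may never be randomized. The fitting visit would then act as an unplanned run-in.
2. If randomization comes first, the person is in the Intent to Treat population but has no self-fit score. MAR imputation supplies one, from a model whose self-fit values all come from people who produced a self-fitting.

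Inability to complete the self-fitting can occur only under one of the two treatments, so either route moves the comparison towards non-inferiority. At stake is whether the result describes everyone who tries the method or only those who managed it.

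**Working it through.** **Inputs from section 9.** Planned difference (self minus professional) -5.0, SD of the difference 14, margin -12.5, one-sided alpha 0.025, power 90%, 40 participants with both scores, 44 enrolled, attrition at most 10%.

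**Assumed inputs.** The documents give neither of these:
- *f*, the share unable to self-fit: 5% and 10%. The upper value uses up the plan's entire attrition allowance.
- *B*, the professional-fit benefit in those people: 15, 20 and 25 points. They are taken to have no self-fit benefit, so their mean difference is -B.

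**Step 1: the plan's sample size.** The distance to the margin is 12.5 - 5.0 = 7.5. The normal approximation gives (14 × (1.960 + 1.282) / 7.5)² = 36.6, so 37. The noncentral t with n - 2 degrees of freedom gives 39 for 90% power, and power 0.910 at n = 40. The planned 40 is sound.

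**Step 2: pass threshold.** SE = 14/√40 = 2.214 and t(0.975, 38) = 2.024. With the SD at its planned value, the trial passes if the estimate exceeds -12.5 + 2.024 × 2.214 = -8.02.

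**Step 3: error rate at the margin.** Let *d* be the true difference among people who can self-fit. The all-comer difference is D = (1 - f)d - fB. Setting D = -12.5 gives d = (-12.5 + fB)/(1 - f). If failures are omitted, or imputed so that they resemble the rest, the analysis estimates *d*. The pass probability is from the noncentral t, 38 degrees of freedom.

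| f | B | d | P(pass), nominal 0.025 |
|---|---|---|---|
| 5% | 15 | -12.37 | 0.029 |
| 5% | 20 | -12.11 | 0.037 |
| 5% | 25 | -11.84 | 0.047 |
| 10% | 15 | -12.22 | 0.033 |
| 10% | 20 | -11.67 | 0.056 |
| 10% | 25 | -11.11 | 0.089 |

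**Step 4: bias at the planned effect.** With d = -5, D = -5(1 - f) - fB:
- f = 5%: -5.5, -5.75 and -6.0 for B = 15, 20 and 25.
- f = 10%: -6.0, -6.5 and -7.0.

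The analysis would report about -5. All six values are inside -12.5.

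**Step 5: would the conclusion change?** Take 40 completers observed at exactly -5 with SD 14, and 4 failures fixed at -15, -20 or -25. The lower 95% limit is then -10.1, -10.6 or -11.2, so non-inferiority still holds. For the limit to reach -12.5, the non-completers would need a common difference of about -54.7 (2 of 44), -34.5 (4 of 44) or -26.6 (6 of 44).

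**Step 6: power if failures are scored as zero benefit.** With 4 failures among 44, SD 14 in both groups and the others at -5, simulated power is about 0.85, 0.78 and 0.69 for B = 15, 20 and 25 (200,000 simulated trials each; smaller runs differ by up to 0.01). With 40 completers and MAR holding around -5 it is 0.91.

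**The case against.** A reader might infer that people who fail or dislike the self-fitting are never randomized or are replaced by successes, so that the trial cannot meet its objective. The documents do not support that reading.

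- **Timing.** Nothing says that unsuccessful self-fitters are excluded before randomization, and no run-in is described. The timing is simply not stated.
- **Attenders.** The APHAB is scheduled for everyone at appointments 3 and 4, and nothing makes it conditional on wear or satisfaction. Someone who tolerates the device poorly but attends contributes an observed score, and the Intent to Treat definition keeps it. This is probably the commonest kind of poor outcome.
- **Abandonment.** A poor-sounding device can be given up under either fitting. Only inability to complete the self-fitting is specific to one treatment.
- **Imputation.** Chained equations can use the participant's own other scores, so an imputed value is not merely a copy of a success. The model still has no self-fit score from anyone whose fitting failed.
- **Sensitivity analysis.** A pattern-mixture analysis is planned. It is under-specified, and it cannot recover people who were not randomized.
- **Rarity.** Section 3 describes set-up as choosing a sound profile in an app, and section 7 requires the ability to use a smartphone. Complete failure may be uncommon, and assigning all 10% attrition to it is an extreme case.

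These objections narrow the point to participants with no usable self-fitting. For them the gap remains: the plan fixes neither whether they are counted nor how.

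**Conclusion.** The concern holds in this limited form. Followed as written, the plan allows a participant with no usable self-fitting to be left out or modelled on people who had one, and both favour non-inferiority.

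The size cannot be determined from the documents. Under the assumed 5-10% failure and 15-25 points of professional-fit benefit, the error rate at the margin is about 0.03-0.09 instead of 0.025. That inflation applies when the all-comer difference lies exactly at the margin. At the planned effect the bias is 0.5 to 2.0 points and does not reverse the conclusion. With few or no failures the trial can meet its objective, so it would be wrong to say that it cannot show non-inferiority. This is an inexpensive improvement to make before data are seen; it does not invalidate the design.

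**What to change.** 1. **Randomize after eligibility is confirmed and before any fitting at appointment 1.** Everyone who attempts the self-fitting is then in the Intent to Treat population. Allocation sets only the order, so it can stay concealed until devices are dispensed.
2. **In the primary analysis, score a condition in which no usable fitting could be completed as zero benefit.** Set the aided score equal to the unaided score already collected on day 1. Apply the same rule to both treatments and both endpoints, and define a usable fitting in advance. Keep MAR imputation for other missing scores.
3. **Make the pattern-mixture sensitivity analysis concrete.** As one stated scenario, also score as zero benefit those who abandon a device because of poor hearing with it and have no visit score. Doing this in the primary analysis would be a debatable choice of estimand, so it belongs here.
4. **Report the number unable to complete the self-fitting.**

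The cost is protocol and SAP wording plus one reason-for-missing field on the case report form, with no extra visit. The drawback is real: if failures occur, the self-fit result will be less favourable and power lower (step 6 of the working). Holding 90% power against that possibility would need more than 44 participants.
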